#### 5.1.6 Surgical Quality Assurance Reviews

5.1.6.1 The study chair, [name], PhD, and designated Surgical Quality Assurance co-Chairs will review surgical preoperative eligibility criteria and operative reports for both the transoral endoscopic resection as well as the neck dissection(s) (i.e., the Operative and Surgical Pathology reports for the initial evaluation of lymph nodes and the surgical resection).

5.1.6.2 [name] will perform a Quality Assurance Review after complete data for the first 15 cases enrolled has been received at ECOG-ACRIN Headquarters. [name] will perform the next review after complete data for the next 15 cases enrolled has been received at ECOG-ACRIN Headquarters. The final cases will be reviewed within 3 months after this study has reached the target accrual or as soon as complete data for all cases enrolled has been received at ECOG-ACRIN Headquarters, whichever occurs first.

#### 5.1.6.3 Goals of Surgical Quality Assurance

- To assure eligibility and correct surgical staging of patients;
- To assure safety of patients undergoing resection
- To assure adequate resection of primary tumor and neck dissection

#### 5.1.6.4 Surgical Protocol Compliance Criteria

Deviations Minor:

- "Close" margin, (< 3mm)
- suboptimal neck dissection (< 20 nodes removed)

Deviations Unacceptable: Those deviations that affect patient safety/outcome, which will result in an institution being suspended from further participation in the study, such as:

- Positive Margin rate exceeding 20% (assessed every 5 cases accrued)
- Inadequate nodal dissection (< 15 nodes removed)

Rev. 2/14

- Postoperative bleeding requiring return to the operating room for control, exceeding 20% of submitted patients (assessed every 5 patients accrued)

### 5.1.7 Pathologic Analysis of Surgical Specimens

Within RTOG / ECOG-ACRIN centers, a designated surgical pathologist will be responsible for quality control of surgical pathology material processing, evaluation and reporting at their respective institution.

Histopathologic Assessment: Histopathologic assessment of surgical pathology frozen and permanent sections must include examination and reporting of the following parameters:

- Perineural invasion (PNI) and lymphovascular invasion (LVI)  
Absent, or Present
- Extracapsular extension (ECE) requires gross and microscopic assessment
  - *absent* (negative or nodal metastasis with smooth/rounded leading edge confined to thickened capsule/pseudocapsule),
  - *present - minimal* (tumor extends  $\leq 1$  mm beyond the lymph node capsule), or
  - *present - extensive* (tumor extends  $> 1$  mm beyond the lymph node capsule (includes soft tissue metastasis)

p16 Immunohistochemistry (must be performed in a CLIA-certified laboratory); p16 antibody obtained from Roche mtm laboratories AG (CINtec® clone E6H4™) is recommended.

Rev. 1/16

- *negative* (cytoplasmic immunoreactivity noted in  $< 70\%$  of tumor cells), and
- *positive* (cytoplasmic immunoreactivity noted in  $\geq 70\%$  of tumor cells).

Rev. 6/14

Pathology materials are required to be submitted for central review as outlined in Section [11](#).

Rev. 2/15

### 5.1.8 Post-operative Management

Rev. 7/13

**Treatment should start within ten working days after registration to Step 2.**

**The highest risk feature assessed pathologically will determine the patient's category/treatment arm assignment.**

Rev. 2/15

#### 5.1.8.1 Definition of Low-Risk Patient Cohort and Management: Arm A (7 weeks)

Rev. 1/16

Low-risk stratification will require the presence of both primary site and neck dissection low-risk pathologic features, and pathologic stages T1N0, T1N1, T2N0, and T2N1, with no ECS and clear margins ( $\geq 3$ mm). This category will include the absence of close margins ( $< 3$ mm), perineural invasion and lymphovascular invasion in the primary site surgical specimen. Low-risk neck

dissection pathologic features include no more than N1 nodal disease without extracapsular extension.

The adjuvant management plan for low-risk HPV-associated OPSCC patients treated with transoral surgery and neck dissection will be prospective observation.

**Summary of acceptable pathologic stage for “low risk” Arm A:**

**T1-2N0-1, with clear ( $\geq 3$ mm) margins, and without any ECE or PNI/LVI.**

Rev. 2/15

5.1.8.2 Definition of High-Risk Patient Cohort and Management: Arm D (5-7 weeks)

High-risk stratification will be applied when the presence of primary site or neck dissection high-risk pathologic features are identified. High-risk primary site pathologic features will include a positive surgical margin or the presence of “extensive” ( $> 1$ mm) ECE (i.e. *present – beyond minimal*). Within the context of this protocol, only patients with tumor that extends  $> 1$  mm beyond the lymph node capsule (including soft tissue metastasis) will be considered for concurrent cisplatin.

Patients with extensive N2b neck disease ( $\geq 5$  metastatic lymph nodes) regardless of primary tumor margin status will also be considered high-risk.

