**Summary of acceptable pathologic stage for “high risk” Arm D:**

- **Any one of the following features constitutes “high risk” status and will assign the patient to Arm D.**
- **Any T stage with positive margin(s), meaning tumor at the specimen edge that is not superceded by an additional, tumor free margin**
- **“Extensive” ( $> 1$ mm) ECE**
- **$\geq 5$  metastatic lymph nodes) regardless of primary tumor margin status.**
- **Please contact the PI, [name] with any questions or to clarify.**

The adjuvant management plan for high risk HPV-associated oropharyngeal carcinoma patients treated with transoral surgery and neck dissection will be concurrent postoperative CRT to 66 Gy in 33 daily fractions. Concurrent cisplatin will be administered at a dose of 40 mg/m^2 on days 1, 8, 15, 22, 29, 36, 43.

Rev. 6/14, 2/15

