**Summary of acceptable pathologic stage for “intermediate risk” Arms B or C – randomized RT dose:**

- **Any one of these features constitutes “intermediate risk” status and will assign the patient to Arm B or C.**
- **Any T stage with one or more “close” (<3mm) margin(s)**
- **“Minimal” ( $\leq 1\text{mm}$ ) ECE**
- **1 or more lymph node >3cm in diameter (N2a neck disease).**
- **2-4 lymph nodes positive, any diameter  $\leq 6\text{cm}$  (N2b neck disease), regardless of primary tumor margin status.**
- **perineural invasion**
- **lymphovascular invasion**
- **Please contact the PI, [name] with any questions or to clarify.**

Rev.1/16

The adjuvant management plan for intermediate risk HPV-associated OPSCC patients treated with transoral surgery and neck dissection will be postoperative RT alone. Patients will be randomized to either 60 Gy or 50 Gy fractionated daily over 30 or 25 fractions, respectively. For all patients, bilateral cervical nodal chains and the primary site will be irradiated. For selected patients randomized to 60 Gy, the ipsilateral nodal regions involved with carcinoma and the primary surgical site will receive a 10 Gy boost to a total of 60 Gy

Rev.1/16

Rev. 2/15

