#### 5.1.11.2 Guidelines for Target Volume Delineation

- CTV-P60: CTV-P60 will represent the primary **invasive tumor base**. As the surgery will be transoral, the need to comprehensively treat the surrounding normal tissues that would otherwise be at risk for tumor seeding is not a major consideration. The primary factor influencing the delineation of the CTV-P60 volume should be influenced by the intra-operative assessment of the invasive base of the tumor. These findings should be compared to the preoperative imaging to reconcile any discrepancy. CTV-P60 should **not** include the preoperative intra-luminal extent of the primary tumor that did not invade the oropharyngeal mucosa. This volume shall include a 3-5 mm margin of uncertainty around the estimated extent of the invasive tumor base that is deemed at risk.
- CTV-N60: CTV-N60 will represent the dissected cervical nodal volume found to have nodal metastases. This nodal volume will include the peripheral extent of the sternocleidomastoid muscle laterally and medially, will include a portion of the levator scapulae and the scalene muscles.
- CTV-N50: CTV-N50 will represent the either dissected cervical nodal volumes found not to have nodal

metastases or the undissected contralateral cervical neck when it is treated. This nodal volume will include the peripheral extent of the sternocleidomastoid muscle laterally and medially, will include a portion of the levator scapulae and the scalene muscles. Anteriorly, the posterior aspect of the submandibular gland and the medial pterygoid muscle will be the anterior boundary of level II nodal region.

- a. For the ipsilateral dissected neck, CTV-N50 should be extended to nodal volumes adjacent to pathologically involved nodal volumes. For example, if the neck dissection reveals nodal metastases in level II, the adjacent level I and level V should be included in CTV-N50. This nodal volume will include the peripheral extent of the sternocleidomastoid muscle laterally and medially, will include a portion of the levator scapulae and the scalene muscles.

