- b. Indications for inclusion of the lateral retropharyngeal lymph nodes include the presence of ipsilateral level II nodal metastases or primary tumor extension to involve the posterior pharyngeal mucosa or suspected to be at risk due to involvement of the posterior tonsil pillar mucosa. The ipsilateral lateral retropharyngeal lymph nodes lie medial to the internal carotid artery and are predominantly located at the level of C1 vertebral body and occasionally at the C2 vertebral body level. The medial retropharyngeal lymph nodes are not to be delineated.
- c. The contralateral retropharyngeal lymph nodes will be delineated as part of CTV-N50 when there is clinical/pathologic findings of ipsilateral retropharyngeal lymph node metastases.
- d. For the contralateral undissected neck, CTV-N50, the nodal volume should include the contralateral level II, III and IV nodal regions beginning at the level of the posterior digastric muscle. This nodal volume will include the peripheral extent of the sternocleidomastoid muscle laterally and medially, will include a portion of the levator scapulae and the scalene muscles.
- e. Ipsilateral neck will be permitted, ie. omitting the contralateral CTV-N50 when the mucosal invasive base of the tumor is > 1 cm from the midline mucosa as judged at the time of the surgery. For base of tongue cancers, the primary tumor adverse pathologic features including the positive surgical margins should not be present on the medial tumor

specimen. For base of tongue cancers, the primary tumor should also not demonstrate a deep invading tumor front at the time of the surgery. The distance from the midline mucosa will require documentation including the mucosal surface that is involved when the contralateral CTV-N50 is omitted. Omitting the contralateral neck CTV-N50 is not permitted for N2c tumors and where clinical/pathologic findings of ipsilateral retropharyngeal lymph node metastases.

- CTV-P66: CTV-P66 will represent the region in the primary tumor bed deemed to be at risk due to the presence of a positive involved surgical margin. Typically, this will be at the deep surgical resection margin and thus will not be significantly extending into the pharyngeal lumen.

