- CTV-N66: CTV-N66 will represent the region in the dissected neck found to have grade 4 ECE. This volume should include sternocleidomastoid muscle in the nodal levels found with ECE *present - beyond minimal* (tumor extends > 1 mm beyond the lymph node capsule (includes soft tissue metastasis).
- CTV-P70 or CTV-N70: CTV-P70 or CTV-N70 will represent postoperative gross tumor that requires treatment to 70 Gy.

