#### 5.1.12 IMRT Prescription and Treatment Planning

5.1.12.1 The prescription dose will be administered with a cone-down prescription with daily doses of 2 Gy. No simultaneous in-field boost / dose-painting will be permitted. Treatment will be delivered once daily, 5 fractions per week. Treatment breaks, if necessary, should not exceed 5 treatment days and the reason(s) for the break must be clearly recorded in the treatment record. Any treatment break(s) exceeding two (2) treatment days for reasons other than toxicity/illness will be considered a protocol deviation. The reason for the missed treatment or treatments must be clearly indicated in the copy of the patients treatment record submitted to IROC Rhode Island.

- PTV-N50: will be prescribed 50 Gy in 25 daily fractions
- PTV-P60 or PTV-N60: will be prescribed 60 Gy in 30 daily fractions
- PTV-P66 or PTV-N66: will be prescribed 66 Gy in 33 daily fractions
- PTV-P70 or PTV-N70: will be prescribed 70 Gy in 35 daily fractions

As a cone-down IMRT technique will be used, a dose-summary that represents all the phases of IMRT treatment

planning shall be generated. For example, if the maximum PTV prescription for a patient is to PTV-P66, then the first phase will deliver 50 Gy to both the primary and unilateral (see section 5.1.11.2.e) or bilateral cervical nodal volumes followed by a second phase to the primary surgical bed for an additional 10 Gy and a third phase to the just the boost volume at the site of the positive surgical margin for an additional 6 Gy.

- 5.1.12.2 Tissue Heterogeneity: The dose calculation shall take into account the effect of tissue heterogeneities. The method used for tissue heterogeneity calculations shall be reported. The dose prescription is to be based on a dose distribution corrected for heterogeneities.
- 5.1.12.3 No specific beam arrangements will be specified. Commonly, a co-planar beam arrangement is used.
- 5.1.12.4 Treatment Planning Objectives: The treatment plan(s) used for each patient will be based on an analysis of the volumetric dose, including dose-volume histogram (DVH) analyses of the PTVs and critical normal structures. Inverse optimization algorithms will be used to achieve at least 95% of the volume of the specified PTVs is covered by the prescribed isodose surface while meeting the dose limitations to the delineated OARs.

Priority	Structure Name	Treatment Planning Objective				

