5.1.18 Administration of cisplatin

Patients on Arm D will receive cisplatin 40 mg/m^2 as an IV infusion in normal saline over 60 minutes weekly (Days 1, 8, 15, 22, 29, 36, 43) during 7 weeks of radiation therapy. Cisplatin administration outside of these specified days during radiation is only allowed in the event of holidays that do not permit drug and radiation delivery on the specified date. Subsequent chemotherapy doses should follow the protocol specified days of treatment. No cisplatin will be prior to day 1 of radiation therapy. In the event that radiation therapy is held, no cisplatin will be administered during the week of the radiation break.

**The use of colony stimulating factors (G-CSF, GM-CSF) and amifostine in this trial is explicitly discouraged. Erythropoietin stimulating agents, such as erythropoietin and darbepoietin, are prohibited.**

- Cisplatin administration should be accompanied by vigorous forced hydration (1000ml delivered over 1-2 hours just prior to treatment, and immediately after treatment) and Mannitol diuresis. Hydration/diuresis may be adjusted where clinically indicated at the discretion of the investigator, or according to standard institutional or regional practice. Potassium chloride and/or magnesium sulfate may be added to the hydration solutions per institutional practice. Magnesium wasting is a well-known complication of cisplatin therapy.
- Routine premedication should include a 5 – HT3 receptor antagonist and dexamethasone. Aprepitant is encouraged for prevention of severe nausea, and should be administered on the

following schedule: aprepitant 125mg orally day 1, aprepitant 80 mg orally day 2, day 3

- Careful attention should be paid to urine output with supplemental fluids or diuretics given as appropriate. Serum potassium and magnesium levels should also be monitored regularly.
- Regular administration of aminoglycoside antibiotics, iodinated CT contrast, or other nephrotoxic agents within 48 hours of cisplatin should be avoided in view of their potentiating effect on cisplatin nephrotoxicity.
- Aluminum-containing needles should not be used for cisplatin administration.

Rev. 2/14

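### Section 5.1.8.2 limits cisplatin to ECE above 1 mm although four other statements give it to all of Arm D, and for patients in Arm D by node count alone the 66 Gy arm dose conflicts with the volume rules

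*Combined protocol and SAP*

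**What the plan says.** **Cisplatin.** Section 5.1.8.2 assigns a patient to Arm D for any single one of three features: a positive margin, ECE beyond 1 mm, or at least five metastatic nodes. Directly after the ECE criterion it states that "only patients with tumor that extends $> 1$ mm beyond the lymph node capsule (including soft tissue metastasis) will be considered for concurrent cisplatin". The same section closes with the management plan for high-risk patients, which "will be concurrent postoperative CRT to 66 Gy in 33 daily fractions", with weekly cisplatin 40 mg/m² and no ECE condition. Section 5.1.18 says "Patients on Arm D will receive cisplatin", again without a condition. The opening of Section 9 and Section 9.8 give high-risk patients cisplatin plus 66 Gy.

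**Dose and volumes.** Section 5.1.11.2 defines two 66 Gy volumes. For the primary site, "CTV-P66 will represent the region in the primary tumor bed deemed to be at risk due to the presence of a positive involved surgical margin". For the neck, "CTV-N66 will represent the region in the dissected neck found to have grade 4 ECE", which the next sentence ties to extension beyond 1 mm. The 60 Gy nodal volume is broader: "CTV-N60 will represent the dissected cervical nodal volume found to have nodal metastases". Section 5.1.12.1 prescribes 66 Gy to the first pair and 60 Gy to the 60 Gy volumes. Its worked example, for a patient whose maximum prescription is PTV-P66, ends with "a third phase to the just the boost volume at the site of the positive surgical margin for an additional 6 Gy".

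**The concern.** A treatment rule inside the section that defines Arm D conflicts with the plan printed a few lines later. A site that follows the restrictive sentence would withhold chemotherapy from a patient whom the rest of the protocol treats with it.

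The dose question is quieter. A planner with a patient who has, say, six positive nodes, clear margins and no extensive ECE finds 66 Gy in the arm prescription and 60 Gy in the volume definitions. Two sites could answer differently in good faith, and radiotherapy quality review would have no single standard to judge them by.

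Arm D is the comparator for Arms B and C in the primary quality-of-life analysis and the toxicity tests (Section 9.5) and in the exploratory two-year PFS comparisons (Section 9.3). What Arm D received therefore has to be clear.

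**Working it through.** **1. Rules side by side, by route into Arm D**

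| Sole qualifying feature | Restrictive sentence in 5.1.8.2, read literally | 5.1.8.2 plan, 5.1.18, Section 9 opening, 9.8 | 66 Gy volume in 5.1.11.2 |
|---|---|---|---|
| ECE beyond 1 mm | cisplatin considered | cisplatin | CTV-N66 |
| Positive margin | not considered | cisplatin | CTV-P66 |
| Five or more nodes | not considered | cisplatin | none; CTV-N60 fits |

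The cisplatin rules disagree in two rows of three. Four statements support treating everyone. Section 8.1.5 is consistent with them but weaker: it confines cisplatin to Arm D without saying that every Arm D patient receives it.

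**2. Dose for node count alone**

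- Arm rule: 33 × 2 Gy = 66 Gy.
- Volume rule (CTV-N60): 30 × 2 Gy = 60 Gy.
- Difference: 6 Gy, or 6/66 = 9.1% of the arm dose.

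The documents point both ways on which was meant.

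- *For 66 Gy:* the arm prescription has no exception. Section 5.1.18 schedules cisplatin on day 43, whereas 30 fractions from a Monday start without breaks end on day 40. The volume label is also not decisive: the CTV-N60 wording equally describes a node-positive Arm B patient, who receives 50 Gy.
- *For 60 Gy:* Section 1.4 names a positive margin and nodal ECE, not node count, as warranting at least 63 Gy.

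For the 60 Gy arm, Section 5.1.8.3 says where the boost goes: "the ipsilateral nodal regions involved with carcinoma and the primary surgical site will receive a 10 Gy boost to a total of 60 Gy". Arm D has no equivalent for node-count-only patients.

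**3. Size of Arm D**

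Inputs are 515 registrations and 73% evaluable (Section 9.2), with 32% of evaluable patients high risk (Section 9.3). 515 × 0.73 × 0.32 = 120.3, which reproduces the stated figure of about 120. No split by qualifying feature is given, so the count affected cannot be derived.

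**4. The pN2c/N3 fallback**

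Under Sections 9.1 and 9.3, two or more events among the first 10 such patients within a year move this group to 66 Gy plus cisplatin. By the opening of Section 9 they have no high-risk feature, so they too lack a 66 Gy volume.

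Inputs: the group is 5% of the population (Section 9.3), accrual is 18.5 per month (Section 9.2), and the rule is assessed once the 10th patient has one year of follow-up. Accrual during that year is 12 × 18.5 = 222.

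- 5% of registrations: 10/0.05 = 200; 200 + 222 = 422; 515 − 422 = 93 left; 93 × 0.05 = 4.7 patients.
- 5% of evaluable patients: 10/(0.05 × 0.73) = 274; 274 + 222 = 496; 19 left; 19 × 0.0365 = 0.7 patients.
- If the Arm C assignment began only after the first 69 registrations (an assumption from the February 2015 revision mark beside Section 5.1.8.4 and the 59 + 10 patients counted in Section 9.4): 69 + 200 + 222 = 491, leaving 24 × 0.05 = 1.2. On the evaluable basis, 69 + 274 + 222 = 565 exceeds 515, leaving none.

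This gives about 0 to 5 later registrants, and only if the rule fires. Patients registered but not yet irradiated could add at most 2 to 3: 4 + 7 + 2 weeks is about 3 months, and 3 × 18.5 × 0.0365 to 0.05 gives 2.0 to 2.8.

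**The case against.** The strongest reply on cisplatin is that context settles the meaning. The sentence follows the ECE criterion and precedes the one that adds node count. Section 1.3 discusses sparing patients with microscopic ECE from cisplatin. The bold summary makes any one feature sufficient, and investigators are told to ask if unsure. This stands as an account of intent, and cisplatin for all of Arm D is the likely practice. A reader might infer that margin-only and node-only patients would lose the full 7 × 40 = 280 mg/m². The documents do not support that as an expected effect. What remains is a rule that says something other than what was meant.

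On dose, a reader might infer that the target of the last 6 Gy is simply undefined. That is too strong: there are two candidate answers, 66 Gy from the arm rule and 60 Gy from the volume rule. The worked example in Section 5.1.12.1 does not help, since it covers only a positive-margin patient.

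A reader might also infer that delivering 60 Gy would be a minor deviation, because 9.1% lies between 5% and 10%. This does not follow either. Section 5.1.17 measures dose against the prescription volume, and if the patient has no 66 Gy volume, 60 Gy to PTV-N60 is on specification.

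Finally, Arm D is assigned by risk and not randomised, so comparisons with it are confounded in any case. That is true and limits the statistical consequence. It does not remove the need for one rule on what Arm D patients receive.

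**Conclusion.** The cisplatin sentence is wrong as written and contradicts four statements elsewhere in the plan. The conflict is one of wording in a treatment rule; no loss of treatment should be predicted from it. The dose conflict for patients in Arm D by node count alone is real but secondary: 66 Gy by arm against 60 Gy by volume, a difference of 6 Gy. Which is right is a clinical decision that the documents do not settle.

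The affected share of the roughly 120 Arm D patients cannot be computed. The fallback adds about 0 to 5 later registrants if its rule fires, assuming constant accrual and the 5% share. The consequence is for consistent treatment within Arm D and for the secondary and exploratory comparisons with it. The primary analysis of Arms B and C, the sample size and the stated power figures do not change.

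**What to change.** **Cisplatin.** In Section 5.1.8.2, delete the restrictive sentence or replace it with: *Minimal (≤1 mm) ECE alone does not qualify for concurrent cisplatin.* Sections 5.1.18, 8.1.5, 9 and 9.8 then need no change on this point.

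**Dose.** The radiation oncology lead should state in Section 5.1.11.2 which rule governs patients with five or more nodes but neither a positive margin nor ECE beyond 1 mm.

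- Option A: define a CTV-N66 for them.
- Option B: declare 60 Gy their intended maximum. The Arm D plan in Section 5.1.8.2 must then be amended, with the 66 Gy statements in Sections 9 and 9.8 and the day-43 cisplatin dose brought into line.

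The same statement should cover pN2c/N3 patients treated under the Section 9.3 fallback. If 60 Gy is chosen for them, the fallback wording in Sections 9.1 and 9.3 changes too.

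**Cost.** One reworded sentence, one volume statement with radiation oncology sign-off, and matching edits if Option B is chosen. No extra patients, procedures or data fields are needed. If Arm D treatment is already complete, the same clarification is still needed for radiotherapy review and for reporting what the arm received.
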